7.8.2 Handling of withdrawals and losses to follow-up

Suggested dosing schedule for withdrawal:

Although there is limited information, abrupt withdrawal of CBD has not been associated with any withdrawal-type symptoms. Because information is limited it is suggested that the dose be reduced by 10% each day until ceased. If a severe serious adverse event (SAE) occurs then the dose may need to be stopped immediately. Abrupt termination of CBD is not recommended, as there is a potential for status epilepticus or a marked deterioration in seizures. This is not a specific reported problem with CBD but a general principle that applies to anticonvulsant management.

When a patient withdraws from the CAS, they will need to complete their final monitoring, as per Section 7.7

7.8.3 Replacements

The AP will notify the PO of any withdrawals. The PO will determine the next patient in-line to be invited to participate, and contact their AP.

7.9 CAS Closure

The PO will notify the APs of any known or upcoming changes to the supply of Epidiolex[®], including the submission of a registration application by GW Pharmaceuticals to the TGA. Patients participating in the CAS will be notified by their AP of expected CAS closure timeframes.

8. ADVERSE EVENTS AND RISKS

8.1 Definitions

Adverse Events

Any untoward medical occurrence in a patient or clinical investigation subject administered a pharmaceutical product and which does not necessarily have to have a causal relationship with this treatment.

An adverse event (AE) can therefore be any unfavourable and unintended sign (including an abnormal laboratory finding, for example), symptom, or disease temporally associated with the use of a medicinal product, whether or not considered related to the medicinal product.

Surgical procedures are not AEs; the reason for the surgical procedure is the AE. Elective

hospitalisations for pre-existing conditions are not considered as SAEs.

Adverse drug reaction (ADR)

For unapproved medicines: all noxious and unintended responses to a medicinal product related to any dose should be considered adverse drug reactions.

The phrase 'responses to a medicinal product' means that a causal relationship between a medicinal product and an adverse event is at least a reasonable possibility, i.e. the relationship cannot be ruled out.

Unexpected Adverse Drug Reaction

An adverse reaction, the nature or severity of which is not consistent with the applicable product information

(e.g., Investigator's Brochure for an unapproved investigational product or Product information/Package Insert/Summary of Product Characteristics for an approved product)

Serious Adverse Event (SAE) or Serious Adverse Drug Reaction (Serious ADR)

Any untoward medical occurrence that at any dose:

- Results in death;
- Is life-threatening*;
- Requires in-patient hospitalisation or prolongation of existing hospitalisation;
- Results in persistent or significant disability/incapacity; or
- Is a congenital anomaly/birth defect
- Is medically significant**.

*Note: the term 'life-threatening' in the definition of 'serious' refers to an event in which the patient was at risk of death at the time of the event; it does not refer to an event which hypothetically might have caused death if it were more severe.

**Medical and scientific judgment should be exercised in deciding whether SAE reporting is appropriate in other situations. Important medical events may not be immediately life threatening or result in death or hospitalisation but may jeopardise the participant or may require intervention to prevent one of the other outcomes listed in the definition above. These should also usually be considered serious. Examples are intensive treatment in an emergency room or at home for allergic bronchospasm; blood dyscrasias, prolonged status epilepticus events or the development of drug dependency.

Suspected Unexpected Serious Adverse Reaction (SUSAR)

A SUSAR is any SAE that is both suspected to be related to the investigational product and is unexpected (i.e. not consistent with applicable product information - the Development Core Safety Information section of the Investigator Brochure).

8.2 Assessment and documentation of adverse events

For the purposes of the CAS the Authorised Prescriber is responsible for the recording of all Adverse Events, regardless of their relationship to study drug, with the following exceptions:

- Conditions that are present at screening and do not deteriorate will not be considered adverse events.
- Abnormal laboratory values will not be considered adverse events unless deemed clinically significant by the investigator and documented as such.

AEs will be reviewed for each patient at their scheduled visit and during unscheduled visits including phone calls from patients/parents and relevant health professionals. During the visit the AP or Study Coordinator will collect the following information from the patient:

The description of each AE will include:

- A description of the AE (Diagnosis of Syndrome only [if known] or signs/symptoms);
- The date started, stopped, as well as duration if <24hrs;
- Epidiolex® total Daily Dose at Time of Event;
- Outcome (recovered, recovered with sequelae, continuing, death);
- Severity (mild, moderate or severe);
- Plausible relationship to medication (Yes/No);
- Any action taken, (e.g. treatment, follow-up tests);
- Is it an SAE? If yes, reason.

Where required information is unavailable during the visit, a follow-up will be made by the AP as soon as practicable to complete the AE record.

If the AE is determined to be an SAE, then the AP will inform the relevant parties as per Table 8.4 Serious Adverse Event Reporting including within the specified timeframes and reporting formats.

The AP or study coordinator will record all AEs in WebSpirit in real-time, or transcribed from hardcopy (see Appendix 3) on a monthly basis, as described in Section 9.1.2. If transcribed from hardcopy, then the hardcopy source documentation is kept in the patient's file.

An AP according to the definition in section 8.1 will assess the seriousness of an AE.

For ongoing fluctuations in the severity of an AE, the most severe assessment should be documented. AEs characterised as intermittent will be documented for each episode. All AEs will be followed to adequate resolution, where possible.

Causality assessment is required for all AEs and SAEs. Causality assessment must only be

assigned by the AP. All cases judged as having a reasonable suspected causal relationship to the Epidiolex[®] must be reported as such. The expression "reasonable causal relationship" is meant to convey in general that there are facts (evidence) or arguments to suggest a causal relationship.

The following question which must be answered by the Physician for all AEs is used to capture the reasonable causal relationship of an event to the Epidiolex[®]:

"In your opinion is there a plausible relationship to the Epidiolex[®]?" The answer is **"yes"** or **"no"**.

Where a pre-treatment event worsens in severity following the first dose of Epidiolex[®] a new event record should be entered into the records.

For all AEs and especially SAEs, it is important that the AP assesses not only the possible role of Epidiolex[®], but also competing etiological factors as the underlying cause (which may include medical history, worsening of underlying condition / lack of efficacy, social or concomitant medication factors).

8.3 Eliciting adverse event information

Adverse events will be recorded from the time the patient signs the informed consent form until 30 days after the last dose of study medication. At every visit patients (or parents, legal guardians) will be asked "How have you (s/he) felt since your (their) last visit?" in order to elicit any medically related changes in their well-being. They will also be asked if they have been hospitalised, had any accidents, used any new medication or changed concomitant medication regimens. In addition, AEs will be documented from physical examination findings, clinically significant lab results or other documents that are relevant to patient safety.

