5.2.1 Inclusion Criteria

Potential patients for inclusion on the CAS must meet ALL of the following:

- Have a clinical diagnosis of severe, intractable childhood epilepsy.
- Be 2 to 18 years of age at the time of consent.
- Experience seizures at least daily for the past six months.
- Have had at least one non-elective epilepsy related hospital admission during 2016. This does not include elective admissions such as epilepsy related investigations or initiation of the ketogenic diet.
- Failure of a clinical trial of at least five anti-convulsant drugs, including one trial of a

combination of two drugs. Vagal nerve stimulation, epilepsy surgery, deep brain stimulation, or ketogenic diet are considered equivalent to a trial of an anti-convulsant drug for the purpose of this inclusion criteria.

- Attempted and failed² an appropriate anticonvulsant where specifically indicated for genetic epilepsy syndromes (e.g. Stiripentol in Dravet syndrome, Vigabatrin for TSC, etc.)
- The dominant seizure type being uncountable, i.e. not suitable for a typical randomized clinical anti-convulsant trial; for example, atypical absence, non-convulsive status, multiple tonic seizure cluster, large number of daily seizures
- Being administered between 1 and 4 baseline anti-epileptic drugs at stable doses for a minimum of 4 weeks prior to enrolment. Vagus nerve stimulator (VNS) and ketogenic diet do not count toward this limit.
- Verbal consent to have certain health information used in determining patient suitability to participate in the CAS.
- Written informed consent obtained from the patient or the patient's parent/guardian.
- Parental/guardian compliance to CAS monitoring requirements including regular blood testing and safety data collection and storage.

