5.2.2 Exclusion criteria

Patients who meet any of the following criteria are not eligible for participation:

- Pre-existing abnormalities of complete blood count, electrolytes, coagulation, hepatic function or enzymes that are considered clinically significant as judged by the Authorised Prescriber (e.g. WBC < 4, Platelets < 60000, ANC < 1.5, ALT or AST > 2 times upper limit of normal)
- Clinically significant ECG abnormalities (e.g. QTc > 460 msec, PR > 0.2 sec, QRS > 0.1 sec)
- Have a terminal illness, with life expectancy not longer than 3 months.
- Use of any cannabis-related product in the month prior to consent
- Female subjects who are pregnant will be excluded. Cannabidiol is contraindicated in pregnancy. If a female subject is able to become pregnant, she will require a negative serum pregnancy test before entry into the scheme. Female subjects will be informed not to become pregnant while taking cannabidiol. Female subjects must inform the investigator and consult an obstetrician or maternal-fetal specialist if they become pregnant during the study.
- Known allergy to CBD or any cannabinoid or any component of Epidiolex[®].

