7.8 Participant Withdrawal

7.8.1 Reasons for withdrawal

Patients are free to withdraw from the study at any time upon their request or the request of their legally acceptable representative. Withdrawing from the study will not affect their access to standard treatment or their relationship with the hospital and affiliated health care professionals.

The patient must be withdrawn from the CAS if any of the following events occur:

- The patient experiences an Adverse Event or Serious Adverse Event which in the opinion of the AP would compromise the continued safe participation of the patient in the CAS
- Develops, during the course of the study, symptoms or conditions listed in the exclusion criteria
- The patient becomes pregnant, as evidenced via a positive pregnancy test
- The patient is unwilling or unable to continue, or the parent/legal representative is unwilling or unable to allow the patient to continue
- The AP decides that withdrawal is in the patient's best interests
- ALT or AST >8xULN
- ALT or AST >5xULN for more than 2 weeks
- ALT or AST >3xULN and (TBL >2xULN or INR >1.5)
- ALT or AST >3xULN with the appearance of fatigue, nausea, vomiting, right upper quadrant pain or tenderness, fever, rash, and/or eosinophilia (>5%)

All patients with elevated LFTs should be followed until all abnormalities return to the baseline state as assessed by the investigator with AST/ALT < 3X ULN.

The Authorised Prescriber may withdraw a patient from the CAS if the patient:

- Does not fulfil the monitoring requirements
- Shows an increase, or no measureable improvement, in seizure frequency and/or severity as assessed by the AP.

The Authorised Prescriber will also withdraw all participants if the CAS is terminated either

due to Epidiolex[®] being registered by the TGA, or in the event GW Pharmaceuticals ceases to supply product.

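### Birth defect is a listed serious event, but adverse event recording ends 30 days after the last dose with no pregnancy exception, so the birth outcome of an exposed pregnancy would ordinarily be missed

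*Protocol*

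**What the plan says.** Five parts of the protocol bear on this.

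- **Who can enrol.** Section 5.2.1 requires that a patient "Be 2 to 18 years of age at the time of consent". Section 5.2.2 adds: "If a female subject is able to become pregnant, she will require a negative serum pregnancy test before entry into the scheme". Patients who could conceive are therefore admitted.
- **Pregnancy during treatment is foreseen.** Section 5.2.2 calls cannabidiol contraindicated in pregnancy. It tells female patients to inform the investigator and to "consult an obstetrician or maternal-fetal specialist if they become pregnant during the study".
- **Withdrawal is compulsory.** Section 7.8.1 states: "The patient must be withdrawn from the CAS if any of the following events occur". One listed event is: "The patient becomes pregnant, as evidenced via a positive pregnancy test". On stopping the product, Section 7.8.2 says "it is suggested that the dose be reduced by 10% each day until ceased".
- **Birth defect is a seriousness criterion.** The list in Section 8.1 includes "Is a congenital anomaly/birth defect".
- **Recording has a fixed end.** Under Section 8.3, adverse events are recorded from signed consent "until 30 days after the last dose of study medication". No exception is given.

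**The concern.** Each rule is unremarkable alone; the difficulty appears when they are applied in sequence. A positive test triggers withdrawal, withdrawal leads to a last dose, and the last dose starts a 30-day clock. For a pregnancy found at any usual time, that clock runs out well before birth, which is when most of the information on a birth defect would arise.

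No other step in the body text picks the pregnancy up. The withdrawal visit (Section 7.6), the unscheduled visit that Section 7.8.2 cites for final monitoring (Section 7.7), the SAE reporting table (Section 8.4) and the table of other reports (Section 8.5) contain no pregnancy item. The outcome categories in Section 8.2 do not fit a pregnancy, and the body text schedules no contact after the withdrawal visit.

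At stake is how a safety summary may be read. The synopsis names safety monitoring as the outcome, and Section 3 gives evaluation of safety in an Australian population as a secondary purpose of the data. A count of zero birth defects could mean that none occurred, or only that nobody was required to ask. The two could not be told apart.

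**Working it through.** The protocol gives no figure of its own to reproduce, so the check is date arithmetic.

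**Inputs from the protocol**
- Recording continues for 30 days after the last dose (Section 8.3).
- The taper is 10% each day until ceased (Section 7.8.2), which can be read in more than one way. An immediate stop, which that section allows for after a severe serious event, gives T = 0 days. Steps of 10% of the starting dose give T = 10 days. Steps of 10% of the current dose never reach zero; taking below 5% of the starting dose as the end (an assumption), T is the smallest whole number with 0.9^T < 0.05. Since ln 0.05 / ln 0.9 = 28.4, T = 29 days.
- The first quarterly visit is at 3 months with a window of 2 weeks either side (Section 7.5).

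**Assumptions, because the body text is silent**
- Term is 40 gestational weeks, that is 266 days after conception plus 2 weeks.
- Detection is at gestational week D = 4 to 17. The late end supposes a test only at quarterly visits and conception just after one: 13 + 2 = 15 weeks after conception, plus 2 = week 17. Section 7 lists the serum pregnancy test without timing, and the 2-week window is stated only for the first visit.

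**Formulas**
- Window closes at week C = D + (T + 30)/7.
- Gap to delivery G = 40 − C.

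| Taper T (days) | (T + 30)/7 (weeks) | C, D = 4 | G, D = 4 | C, D = 17 | G, D = 17 |
|---|---|---|---|---|---|
| 0 | 4.3 | 8.3 | 31.7 | 21.3 | 18.7 |
| 10 | 5.7 | 9.7 | 30.3 | 22.7 | 17.3 |
| 29 | 8.4 | 12.4 | 27.6 | 25.4 | 14.6 |

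The gap therefore runs from about 15 to about 32 weeks. Testing more often would detect pregnancy earlier and so lengthen the gap. For example, Table 9.1 lists laboratory results monthly as well as quarterly. A test every 4 weeks gives D of at most 4 + 2 = 6, and a gap of at least 40 − 6 − 8.4 = 25.6 weeks.

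**When a term birth would fall inside the window.** Setting G = 0 gives D = 40 − (T + 30)/7, which is week 35.7, 34.3 or 31.6 for T = 0, 10 or 29. In days after conception this is 266 − 30 = 236, 266 − 40 = 226 or 266 − 59 = 207. Only a pregnancy first found that late would have its term birth recorded under Section 8.3.

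**What can still fall inside.** The window closes between about week 8 and week 25. An early loss, or an anomaly seen on prenatal investigation before that point, would be within it.

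**The case against.** The best defence is that other text offers routes around the 30-day limit. Section 5.2.2 obliges the patient to tell the investigator. Section 8.3 allows events to be documented from clinically significant laboratory results, and Section 8.2 lets the investigator judge a laboratory value to be an event. A positive test could be recorded that way. Section 8.2 would then have the event followed until it resolves, where that is possible, and Section 8.4 continues follow-up of a serious event until its investigation is complete. Section 8.5 sets no end date for sending an adverse drug reaction to the TGA.

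This stands in part. Each route works only once someone has chosen to record an event or has volunteered the information. Pregnancy is not defined as an adverse event, so no step is required. The adverse event definition in Section 8.1 refers to a patient or subject given a product, which does not clearly cover a newborn. The routes narrow the gap without closing it.

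Three further objections stand in full.
- The appendices (consent form, monitoring schedule, SAE form, withdrawal form) were not available for review and may contain pregnancy items. The point is limited to the body text.
- A general list of seriousness criteria beside a fixed recording window is an omission rather than a contradiction.
- The event should be rare: at most 30 patients are treated at once (Section 5.1), younger patients have second-tier priority (Section 5.2), pregnancy is excluded at entry, and patients are told not to conceive.

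A reader might go further and infer that the birth-defect category can never be filled from an exposure in the scheme, or that pregnancy outcomes are never collected. The documents do not support either reading, given the cases that can fall inside the window, the discretionary routes and the appendices not shown.

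**Conclusion.** The point holds for the body text at low severity. The rules as written would ordinarily leave the birth outcome of an exposed pregnancy outside required adverse event recording. The shortfall of about 15 to 32 weeks rests on assumed detection timing, a 40-week term and the range of taper readings. The direction is robust: no combination considered brings a term birth inside the window unless the pregnancy is first found at about gestational week 32 or later.

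The issue is completeness of safety data. It affects no sample size, error rate or estimate, since the scheme defines no research question.

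**What to change.** Add an exception to Section 8.3 along these lines: *Any pregnancy with exposure to Epidiolex is reported to the Project Office and GW Pharmaceuticals on the SAE timelines and, with consent, is followed to its outcome, including the newborn, regardless of the 30-day limit.* Cross-refer to it from Sections 5.2.2 and 7.8.1. First check the appendices; if one already provides for this, a cross-reference from Section 8.3 suffices.

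The cost is an amendment that needs approval from the HREC and GW Pharmaceuticals under Section 11.1, consent wording that covers follow-up of the pregnancy and newborn, and a rare contact after a patient has left the scheme. The change concerns recording and reporting only; it implies no change to any dose, taper or withdrawal rule.

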8.4 Serious adverse event reporting

The AP is responsible for the reporting of SAEs according to the timelines and reporting requirements below, however, the PO will facilitate reporting once notified.

The AP will make an initial report within the specified timeframes, based on "first awareness" of the SAE, and follow-up as additional information becomes available until the SAE investigation is complete. All SAE submissions are signed/endorsed by the AP even where submitted by a delegate.

AP SAE Timelines and Reporting Requirements

Entity	Initial report within	Report format	Comment
Project Office	Immediately	(hardcopy) GW SAE Australia Form Appendix 4a	As per TGA, CHQHSS is "sponsor". As such CHQHSS reports fatal or life-threatening ADRs (SUSARS) to TGA on "ADRAC Blue Card" (Appendix 5) within 7 calendar days. Follow-up within 8 additional days. For all other serious and unexpected ADRs, (SUSARS) full report no later than 15 calendar days of first knowledge.
GW Pharmaceuticals	24 hours	(hardcopy) GW SAE Australia Form	Project office to facilitate, Requires AP's signature
HREC	72 hours	(online) CHQHHS-SAE form Appendix 4b	Project office to facilitate

Principal investigators at LCCH are responsible for expedited reporting of SUSARs that occur at their site to CHQHHS HREC and CHQHHS Research Governance Office. Expected suspected SAEs should be reported as soon as possible to the CHQHHS Research Governance Office.

The Chief Investigator will, on a six monthly basis, provide CHQHHS HREC an EU format report listing all SUSARs, Australian and International, for Epidiolex® and include any investigator and sponsor comment as to whether any actions are planned for the CAS.

8.5 Other required Adverse Event Reporting (non-SAE)

In addition to the SAE reporting described in Section 8.4, the AP is required to report the following safety information.

Type	Entity	Frequency/Timing	Report format	Comments
Any Adverse Drug Reaction	TGA	As promptly as possible, to reach TGA within 15 days	ADRAC blue card	PO to facilitate
Any AEs	GW Pharmaceuticals	Monthly	GW Pharmaceuticals supplied AE Tabulation	Project office to facilitate

Sponsor AE Reporting Requirements to Regulatory Authorities

Adverse events reporting, including suspected serious unexpected adverse reactions will be carried out in accordance with applicable local and government regulations.

9. DATA MANAGEMENT

9.1 Data Collection

The APs are responsible for ensuring the accuracy, completeness, legibility, and timeliness of the data reported. All source documents should be completed in a neat, legible manner to ensure accurate interpretation of data. All source data will be dated and initialed by the AP prior to submission to the PO. The PO will maintain adequate records of participants, including routine monitoring data and source documentation.

